4. ABSTRACT

4.1 Title

Effectiveness evaluation survey for Eurartesim[™]

4.2 Rationale and Background

The European Medicines Agency (EMA) has requested Sigma-Tau to provide all physicians who are expected to prescribe or use Eurartesim[™] with a healthcare professional educational pack. The EMA has requested Sigma-Tau to perform an Effectiveness survey in order to further assess physician understanding of this education material.

This protocol details strategy consideration for an Effectiveness survey in 3 European countries for physicians who are expected to prescribe or use Eurartesim[™] for the treatment of malaria.

4.3 **Research Question and Objectives**

Primary Objective

• To ascertain the physician understanding of the education material provided about Eurartesim[™], in terms of drug indication, prescription modalities, administration modalities, high-risk patients, and potential side effects.

Secondary Objectives

- To ascertain physician awareness of the pregnancy and safety registries.
- To ascertain physician awareness of available information sources regarding the medication.

4.4 Study Design

Observational, European multi-centre survey, conducted in France, Spain and the United Kingdom (UK).

The survey will be conducted respectively 12 months and 24 months after Eurartesim[™] education material is delivered to the Physicians by the Sponsor.

Physicians will be selected among a list of approximately 300 physicians per country, provided by the Sponsor.

Approximately 60 Physicians per country are expected to participate.

The following selection process will be conducted in each country respectively 12 months and 24 months after Physicians received education material:

- A recruitment mail containing the study summary and a participation form will be sent to all Physicians.
- Physicians will be asked to send back the completed participation form to Mapi. Characteristics of physicians, and if applicable, reason for non participation will be collected on the participation form.
- Non-respondent Physicians will be contacted by telephone by Site Monitor Associates (SMAs), to know if they agree or not to participate in the survey.
- The survey questionnaire will be administered by the SMAs by phone to the Physicians selected for the survey and willing to participate.

4.5 **Population**

Selection criteria:

- Physicians known to treat and follow-up patients with malaria
- Physicians not participating in Pregnancy and Safety registries
- · Physicians who agree to participate in the survey

4.6 Variables

The following data will be collected:

Physician characteristics:

- Specialty
- Geographic location
- Institution type
- Years in practice
- Number of malaria patients currently treated
- Experience with Eurartesim[™] (Number of patients treated the previous year, number of months since last patient treated with Eurartesim[™])

Survey questionnaire:

- Date of questionnaire completion
- Knowledge of the drug
- Reception of education material on Eurartesim[™]
- Indication of Eurartesim[™]
- Prescription modalities
- Administration modalities
- Effects on cardiac repolarization
- High-risk patients
- Potential side effects
- Awareness of the pregnancy and safety registries
- Information sources on Eurartesim[™]

4.7 Data Sources

Data will be collected through a survey questionnaire administered by phone by SMAs to Physicians willing to participate.

4.8 Study Size

Assuming that 20% of Physicians agree to participate in the survey, approximately 60 participating Physicians per country are expected.

4.9 Data Analysis

The statistical analysis will be carried out using SAS software version 9.2.

It will be conducted for 12-month and 24-month surveys, separately, on data collected from all participating Physicians and for each country.

A Statistical Analysis Plan will be prepared by Mapi and approved by the Sponsor before the data-base is frozen.

Analytical methods

Continuous variables will be described by their mean, standard deviation, median, quartiles 1 and 3, extreme values (minimum and maximum) and the number of missing data.

Categorical variables will be described by the total and percentage of each response and the number of missing data. 95% confidence intervals will be computed on each individual percentage.

Description of the study population:

Characteristics of participating Physicians will be described.

Response to the primary objective:

- Knowledge of indication of Eurartesim[™] will be described
- Knowledge of prescription modalities of Eurartesim[™] will be described
- Knowledge of administration modalities of Eurartesim[™] will be described
- Knowledge of effects on cardiac repolarization will be described
- Knowledge of high-risk patients will be described
- Knowledge of potential side effects of Eurartesim[™] will be described

Response to the secondary objectives:

- Awareness of the pregnancy and safety registries will be described
- Awareness of available information sources regarding Eurartesim[™] will be described

4.10 Milestones

Study Milestone	Estimated Date
Ethics submission	July 2013
12-month survey	September 2013 – March 2014
Statistical analyses	May 2014
Interim Study Report	June 2014
24-month survey	September 2014 – March 2015
Statistical analyses:	May 2015
Final Study Report	June 2015

5. AMENDMENTS AND UPDATES

This section is not applicable (original protocol).

6. MILESTONES

Study Milestone	Estimated Date
Ethics submission	July 2013
12-month survey	September 2013 – March 2014
Statistical analyses	May 2014
Interim Study Report	June 2014
24-month survey	September 2014 – March 2015
Statistical analyses:	May 2015
Final Study Report	June 2015
That Olddy Report	00110 2010

7. BACKGROUND AND RATIONALE

7.1 Background

Malaria is one of the most important public health problems in terms of morbidity and mortality, causing more than 200 million cases and 655.000 deaths every year [1].

According to the World Health Organization (WHO) Malaria Report 2011, a total of 106 countries in the world are at risk of transmission of malaria infection. A total of 216 million estimated malaria cases occurred in 2010, 81% of which were reported in the African Region, followed by South East Asia (13%) and Eastern Mediterranean Regions (5%) [1].

Eurartesim[™] (dihydroartemisinin [DHA] - piperaquine [PQP]) is an artemisinin-based combination therapy (ACT), which involves the simultaneous use of two blood schizontocidal medicines with independent modes of action and, thus, different biochemical targets in the parasite. ACT is considered to be often more effective and to prevent or to delay the emergence of resistance [2].

Substantial data are available regarding potential side-effects of the active substances of EurartesimTM (DHA and PQP) alone or in combination in patients [3]. In adults, the most common side-effects observed with EurartesimTM (\geq 1/100 to < 1/10), are anaemia, headache, QTc (corrected QT segment length) prolongation, tachycardia, asthenia and pyrexia. In children, the most common side-effects observed with EurartesimTM use ((\geq 1/10), are influenza, cough and pyrexia [4]. As a result of the findings from animal studies with dihydroartemisinin (DHA), EurartesimTM should not be used during pregnancy if other suitable and effective antimalarials are available. In addition, women should not breastfeed during treatment with EurartesimTM.

In human subjects, small changes in the QTc have been reported after DHA/PQP administration, with no clinically significant cardiotoxicity [5,6]. Evaluation of the torsadogenic risk of DHA and PQP revealed that although there was such a risk, it was lower than for Chloroquine and Halofantrine and in the same range as for Mefloquine and Lumefantrine [7].

In addition, the potential QTc prolongation of Eurartesim^{$^{\text{TM}}$} is significantly reduced when Eurartesim^{$^{\text{TM}}$} is administered in fasting conditions with water [4]. Data indicate that co-administration of Eurartesim^{$^{\text{TM}}$} with fat increases the bio-availability of PQP, which may increase its effect on the QTc interval [8].

7.2 Study Rationale

The European Medicines Agency (EMA) has requested Sigma-Tau to provide all physicians who are expected to prescribe or use Eurartesim[™] with a healthcare professional educational pack containing the following:

- The Summary of Product Characteristics
- The Patient Information Leaflet
- The Physician Leaflet including the Contraindicated Conditions of Use and Contraindicated Concomitant Medication checklist

The Physician Leaflet should contain the following key messages:

- Eurartesim[™] has a potential to prolong the QTc interval that may lead to potentially lethal arrhythmias.
- Piperaquine absorption is increased in the presence of food, therefore to reduce this risk of QTc interval prolongation, the patients should be advised to take the tablets with water, without food, no less than three hours after the last food intake. No food should be taken within 3 hours after each dose.
- Eurartesim[™] is contraindicated in patients with severe malaria according to WHO definition and in patients with a history of clinical conditions that may lead to QTc interval prolongation, and in patients taking drugs that are known to prolong the QTc interval.
- The ECG monitoring recommendations.
- The scope and use of the Contraindicated Conditions of Use and Contraindicated Concomitant Medication checklist.
- There is a potential risk of teratogenicity and so Eurartesim[™] should not be used during pregnancy in situations where other suitable and effective anti-malarials are available.
- Need to counsel patients on important risks associated with Eurartesim[™] therapy and appropriate precautions when using the medicine.
- Patients should be advised to contact their doctor about adverse events and physicians/pharmacists should report suspected adverse reactions to Eurartesim[™], and in particular, those associated with a QT prolongation.
- The existence and scope of the pregnancy register and details of how to enter patients in it.
- In countries where the Safety registry is available, the educational material should include details on the registry and how to enter patients in it.

The EMA has requested Sigma-Tau to perform an Effectiveness survey in order to further assess physician understanding of the education material.

This protocol details strategy consideration for an Effectiveness survey in 3 European countries for physicians who are expected to prescribe or use EurartesimTM for the treatment of malaria.

8. RESEARCH QUESTION AND OBJECTIVES

Primary objective:

To ascertain the physician understanding of the education material provided about Eurartesim[™], in terms of drug indication, prescription modalities, administration modalities, high-risk patients, and potential side effects.

Secondary objectives:

- To ascertain physician awareness of the pregnancy and safety registries.
- To ascertain physician awareness of available information sources regarding the medication.

9. **RESEARCH METHOD**

9.1 Study Design

This is an observational, European multi-centre survey, conducted in France, Spain and the United Kingdom (UK).

The survey will be conducted respectively 12 months and 24 months after Eurartesim[™] education material is delivered to the Physicians by the Sponsor.

9.2 Setting

9.2.1 Physician Selection

9.2.1.1 Selection Criteria

The following Physicians will be included in the study:

- Physicians known to treat and follow-up patients with malaria.
- Physicians not participating in Pregnancy and Safety registries.
- Physicians who agree to participate in the survey.

9.2.1.2 Sampling

Physicians will be selected among a list of approximately 300 physicians per country, provided by the Sponsor.

The following selection process will be conducted in each country respectively 12 months and 24 months after Physician received education material:

- A recruitment mail containing the study summary and a participation form will be sent to all Physicians.
- Physicians will be asked to send back the completed participation form to Mapi. Characteristics of physicians, and if applicable, reason for non participation will be collected on the participation form.

- Non-respondent Physicians will be contacted by telephone by Site Monitor Associates (SMAs), trained for this study, to know if they agree or not to participate in the survey and collect their characteristics, and if applicable, the reason for non participation.

9.2.2 Survey conduct

Approximately 60 Physicians per country are expected to participate.

SMAs will present in details the survey and its process to the physicians who agree to participate and will schedule a telephone appointment to complete the survey questionnaire.

Respectively 12 months and 24 months after Eurartesim[™] education material is delivered to the Physicians by the Sponsor, the survey questionnaire will be administered by the SMAs by phone to the Physicians selected for the survey and willing to participate.

Close-out mails will be sent to the participating Physicians at the end of the 12-month and 24-month surveys.

9.3 Variables

The following data will be collected:

Physician characteristics:

- Specialty
- Geographic location
- Institution type
- Years in practice
- Number of malaria patients currently treated
- Experience with Eurartesim[™] (Number of patients treated the previous year, number of months since last patient treated with Eurartesim[™])

Survey questionnaire:

- Date of questionnaire completion
- Knowledge of the drug
- Reception of education material on Eurartesim[™]
- Indication of Eurartesim[™]
- Prescription modalities
- Administration modalities
- Effects on cardiac repolarization
- High-risk patients
- Potential side effects
- Awareness of the pregnancy and safety registries
- Information sources on Eurartesim[™]

9.4 Data Sources

Data will be collected directly from Physicians, through a survey questionnaire administered by phone by SMAs.

The appropriateness and clarity of the survey questionnaire has been tested through qualitative in-depth interviews with a panel of physicians in all participating countries.

9.5 Study Size

Assuming that 20% of Physicians agree to participate in the survey, approximately 60 participating Physicians per country are expected.

As the analyses will mainly comprise calculations of percentages of correct answers, the expected precision obtained for a given percentage has been calculated using the following formula:

$$e = 1.96 \times \sqrt{\frac{p \times (1-p)}{n}}$$

where n =sample size, p =percentage and e =absolute precision.

The following table presents the precision expected with 60 participating Physicians, considering a two-sided confidence interval of 95% and expected percentages ranging from 10% to 50%.

	р				
	10%	20%	30%	40%	50%
Precision	7.6%	10.1%	11.6%	12.4%	12.7%
Note: This computation is based on large sample normal approximation					

For clarity, assuming for example an expected percentage equal to 30%, the two-sided 95% confidence interval will extend ±11.6% from the observed percentage.

9.6 Data Management

Each document received at Mapi will be tracked at reception and stamped.

Data entry of data collection forms and questionnaires is double data entry except for free text (single data entry). The two data-entries are independent each other, i.e. without knowing the previous entry. All discrepancies detected by the data entry software will be reentered by the same operators. Remaining discrepancies will be flagged to be treated by the data manager during data management process.

A Data Management Plan will be prepared by Mapi and approved by the Sponsor before starting the data entry.

A final validation of the database will be performed and the database locked before statistical analysis is conducted.

9.7 Data Analysis

The statistical analysis will be carried out using SAS software version 9.2.

It will be conducted for 12-month and 24-month surveys, separately, on data collected from all participating Physicians and for each country.

A Statistical Analysis Plan will be prepared by Mapi and approved by the Sponsor before the data-base is frozen.

Analytical methods

Continuous variables will be described by their mean, standard deviation, median, quartiles 1 and 3, extreme values (minimum and maximum) and the number of missing data.

Categorical variables will be described by the total and percentage of each response and the number of missing data. 95% confidence intervals will be computed on each individual percentage.

Description of the study population:

Characteristics of participating Physicians will be described.

To assess the representativeness of participating Physicians, characteristics of participating and non-participating Physicians will be compared. Reasons for non-participation will be described.

Response to the primary objective:

- Knowledge of indication of Eurartesim[™] will be described.
- Knowledge of prescription modalities of Eurartesim[™] will be described.
- Knowledge of administration modalities of Eurartesim[™] will be described.
- Knowledge of effects on cardiac repolarization will be described.
- Knowledge of high-risk patients will be described.
- Knowledge of potential side effects of Eurartesim[™] will be described.

Response to the secondary objectives:

- Awareness of the pregnancy and safety registries will be described.
- Awareness of available information sources regarding Eurartesim[™] will be described.

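### Section 9.7 describes every knowledge item over all participants and does not use the reception item, so the primary percentages may mix reported non-receipt with non-understanding

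*Protocol*

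**What the plan says.** The primary objective (protocol, Section 8) opens: "To ascertain the physician understanding of the education material provided about" the product, and then names the knowledge areas.

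Section 9.2.1.1 gives three selection criteria: "Physicians known to treat and follow-up patients with malaria", "Physicians not participating in Pregnancy and Safety registries" and "Physicians who agree to participate in the survey". None concerns the pack.

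Section 9.3 lists "Reception of education material on Eurartesim" among the questionnaire items.

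Section 9.7 says of the analysis: "It will be conducted for 12-month and 24-month surveys, separately, on data collected from all participating Physicians and for each country". Under the primary objective it lists six knowledge areas, each to be described. None is split by, or limited to, reported receipt. The same section says generally that categorical variables will be summarised by response percentages with 95% confidence intervals.

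Section 9.5 says: "The following table presents the precision expected with 60 participating Physicians". The largest half-width in that table is 12.7 points, at p = 50%.

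Sections 9.1, 9.2.1.2 and 9.2.2 time both survey waves from delivery or receipt of the material, so the design presumes that the listed physicians have it.

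**The concern.** A physician who never saw the pack cannot show understanding of it, although he or she may know some correct answers from elsewhere. Asking about reception makes sense only if some answers may be no. If some are, an all-participant percentage reflects two things: how many physicians report having the pack, and how well those who have it understood it. Only the second is the stated primary objective.

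The distinction matters for action. A low score caused by poor reach points to distribution, and a low score among receivers points to the content of the material. Section 6 places the interim report before the 24-month wave, so a misread 12-month result could carry forward. Section 9.9 discusses selection through voluntary participation and does not mention non-receipt.

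**Working it through.** **Inputs from the protocol.** About 300 physicians listed per country (9.2.1.2); 20% participation, about 60 participants per country, and half-width e = 1.96 × √(p(1 − p)/n) (all 9.5).

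**Inputs assumed.** The protocol gives no receipt rate and no knowledge level by receipt. Let r be the share of participants reporting receipt, pR the proportion correct among them and pN the proportion correct among the rest. All values of r, pR and pN below are illustrations.

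**1. The plan's own figures.** 300 × 0.20 = 60. With n = 60 the formula gives 7.59, 10.12, 11.60, 12.40 and 12.65 points for p = 10% to 50%, against the stated 7.6, 10.1, 11.6, 12.4 and 12.7. The table is correct for 60 participants.

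**2. What the all-participant percentage measures.** It equals r × pR + (1 − r) × pN. With pR = 80%:

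| r | pN = 10% | pN = 30% | pN = 40% | pN = 50% |
|---|---|---|---|---|
| 0.9 | 73% | 75% | 76% | 77% |
| 0.7 | 59% | 65% | 68% | 71% |
| 0.5 | 45% | 55% | 60% | 65% |

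For example, 0.7 × 0.80 + 0.3 × 0.40 = 0.68. In every cell the figure among receivers is still 80%.

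**3. The reverse reading.** Suppose 65% is observed over all participants and pN = 30%. Then pR = (0.65 − (1 − r) × 0.30)/r, which gives 65% at r = 1.0, 74% at 0.8, 80% at 0.7 and 88% at 0.6. The all-participant percentage taken alone fits all four.

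**4. Precision among receivers.** With n = 60r and p = 50%:

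| r | n | half-width (points) |
|---|---|---|
| 1.0 | 60 | 12.7 |
| 0.9 | 54 | 13.3 |
| 0.7 | 42 | 15.1 |
| 0.5 | 30 | 17.9 |

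**5. Precision of a receiver minus non-receiver difference.** The half-width is 1.96 × √(pR(1 − pR)/nR + pN(1 − pN)/nN). With 80% and 40% correct:
- 54 against 6: 1.96 × √(0.16/54 + 0.24/6) = about 41 points.
- 42 against 18: 1.96 × √(0.16/42 + 0.24/18) = about 26 points.

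Per country, such a comparison would be very imprecise.

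**The case against.** **Delivery is presumed.** The survey clock starts at delivery, so the plan does not set out to survey physicians without the pack. This stands. The problem arises only if some participants report non-receipt, and at 90% receipt the shift in the 40% illustration is 4 points. It does not remove the point, because the reception item allows for a negative answer and the plan then makes no use of it in the primary results.

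**The survey can separate the two.** A reader might infer that the survey cannot distinguish a pack that did not arrive from one that was not understood. The protocol does not support that. Reception is collected, and the general rule in 9.7 would have it described as a categorical variable. What is lacking is a link between that answer and the knowledge items.

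**The detail may lie elsewhere.** The statistical analysis plan and the questionnaire routing are not shown, and a breakdown by receipt could appear there. That is fair, but 9.7 itself names the analysis set and lists the primary outputs, and these do not match the objective. If routing skips non-receivers, their answers are not mixed in; the knowledge items then have fewer than the 60 respondents assumed in 9.5.

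**All participants is a defensible denominator.** Section 11.2 presents the study as measuring how well risk management measures work, and knowledge among intended prescribers, reached or not, serves that aim. This stands, and the all-participant figure should stay.

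**Reported receipt is imperfect.** An answer given 12 or 24 months later mixes non-delivery, an unopened pack and forgetting. Limiting the analysis to those who recall the pack may favour better-informed physicians, the direction of bias that 9.9 already fears. This stands, and it argues against making receivers the sole primary set. A reader might also take receivers against non-receivers as evidence of the pack's effect. That does not follow: the groups are self-reported, not randomised and likely to differ in engagement, and step 5 shows how imprecise the difference would be.

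**Conclusion.** The point holds as a mismatch between the objective and the listed analysis. Section 8 asks about understanding of material that was provided, while the primary results in 9.7 are described over all participants without using the reception item. If any participants report non-receipt and answer the knowledge questions, the primary percentages mix the two.

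The size cannot be known from the protocol. Under the assumed 80% and 40% correct, the all-participant figure lies 4, 12 or 20 points below the receivers' figure at 90%, 70% or 50% receipt. At full receipt the two coincide. The precision table is not in error; it describes a denominator that may be larger than the one the objective needs.

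This is a cheap improvement to the analysis section. It is not a flaw in the data to be collected.

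**What to change.** In Section 9.7, for each wave, overall and by country, report side by side:

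1. the percentage reporting receipt of the pack, among all participants;
2. the percentage correct on each knowledge item, among those reporting receipt;
3. the percentage correct on each knowledge item among all participants, retained as now planned.

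Give each with its denominator and 95% confidence interval. Add that reported receipt is subject to recall and may favour better-informed physicians. Any comparison of receivers with non-receivers should be labelled descriptive and not read as the effect of the pack.

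In Section 9.5, state that the 12.7-point worst-case precision applies to 60 participants and is wider among receivers, for example 13.3 points at n = 54, 15.1 at n = 42 and 17.9 at n = 30.

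If the sponsor holds a delivery record by physician, reported receipt can be checked against it. Section 9.4 names no such source, so that check would need data beyond the questionnaire and should be made only if the record exists.

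The three reported percentages need no new question. The cost is a few sentences, a few more tables and wider receiver-only intervals.
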